6.1.4 Follow-up visit week 52 (and for extension study week 104 and 156)

Participants will be invited to the RDU clinic for review of secondary outcomes, or alternatively if hospital attendance is not appropriate due to recommendations to self-isolate or maintain social distancing due to the coronavirus pandemic then this assessment will be made by telephone. The patient diaries generated by the GoutSMART application will be reviewed and any adverse advents recorded. All participants will be asked to record the number of doses of medication missed in the preceding 2 weeks. A physical examination will be performed to assess the size and number of tophi or submitted images will be reviewed. Finger prick and/or serum urate will be measured along with blood tests of renal and liver function tests and oxypurinol levels.

All participants completing the study at week 52 will be offered participation of the extension phase of the study. Written information will have been provided prior to their week 52 review about the extension. Consent will be gained from those choosing to participate in the extension phase. A treatment plan will be formulated for all participants. Participants of the intervention arm in remission will be offered to reduce the dose of their urate lowering medication and self-reassess every two weeks (update urate levels, entering disease activity

data) until remission maintenance is achieved. Feedback will be provided in the usual GoutSMART application manner. Participants of the control arm will continue as per routine care. Once remission maintenance is achieved monthly urate reading will be requested. The participant will be asked to enter additional urate readings and QoL information during flares.

For those opting into the dietary lifestyle intervention arm, a personal management plan with dietary adjustments where appropriate will be formulated based on the Food Frequency Questionnaire which each participant will fill in at baseline. Participants will be asked to perform weekly urate measurements, weight measurements and report on flares via the app. Feedback will be provided by the research team at least weekly for the first 4 weeks, then monthly for three months. Participants will be asked to fill in the Food Frequency Questionnaire at extension baseline, monthly for three months and at the end of study.

A letter will be written to the GP of all participants summarising the disease course and management and proposing further management advice including the information of continued participation in trial if agreed. Participants opting out of participation of the extension phase who have achieved target levels of serum urate will be discharged back to care by their primary care physician. Participants who have not yet achieved control of their serum urate by week 52 will be offered further follow up in the gout clinic in line with usual practice.

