2.2 ENDPOINTS

2.2.1 Primary Endpoint

- Proportion of participants achieving urate level $\leq 0.30\text{mmol/L}$ at 24 weeks.

2.2.2 Secondary Endpoints (assessed at week 24 and 52, and for extension study also at week 104 and 156)

- Proportion of participants achieving urate level $\leq 0.3\text{mmol/l}$ and $\leq 0.36\text{mmol/l}$
- Prospectively gathered number of days of self-reported gout flare over course of study
- Size in mm of the largest tophus at baseline (index tophus)
- The number of clinically evident tophi
- Prospectively gathered self-reported quality of life during/following gout flare evaluated using the EQ-5D-5L questionnaire over course of study
- Prospectively gathered data on days lost at work due to gout flare over course of study
- Prospectively gathered number of scheduled and unscheduled medical appointments/ hospital admissions due to gout over course of study
- Self report of number of doses of medication omitted in preceding 2 weeks will be collected at all study visits
- Plasma oxypurinol levels will be measured at study visits where possible
- Proportion of patients achieving a dose reduction of urate lowering therapy in the extension phase whilst maintaining target urate levels.
- Proportion of patients achieving sustained dietary modifications with reduction of urate levels, and/or further reduction of urate lowering therapy dose in the extension phase.

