Participants that were assigned to usual care will have their care optimised using the GoutSMART approach until they have achieved a urate at or below the target of 0.3mmol/l, but in line with usual clinical practise will have no further titration of their medication or outpatient clinical review after this point. Outcomes will be reviewed at 12 months, 24 months, and 36 months as part of the extension study.

In addition, all patients in the active care arm will be invited to participate in a dietary modification substudy during the extension phase. Those in whom aspects of dietary discordance with current BSR guidelines have been identified utilising the Food Frequency Questionnaire, will be offered an individualised plan of dietary modifications to be implemented over a period of time lasting up to three months. Regular measurements of urate levels and diet feedback will monitor progress.

Figure 2: Study Design Extension Phase

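### In the extension, extra flare reporting is scheduled only for subgroups of the active arm and no common collection is stated after week 52, so flare days may be ascertained unequally between arms

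*Combined protocol and SAP*

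**What the plan says.** **Up to week 52** collection is the same in both arms. Section 6.1.2 prompts every participant monthly for flare days, quality of life, work days lost and health-care appointments. Section 6.1.3 asks for these entries until week 52, and section 6.2.3 describes the app collection as running over the 52 weeks of the study.

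**Endpoints in the extension.** The heading of section 2.2.2 says that the secondary endpoints are "assessed at week 24 and 52, and for extension study also at week 104 and 156". The list includes flare days, work days lost and appointments or admissions due to gout.

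**Reporting in the extension** (sections 3.2 and 6.1.4):

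- Intervention participants in remission who are offered a dose reduction are to "self-reassess every two weeks (update urate levels, entering disease activity" data) until remission maintenance. Then: "Once remission maintenance is achieved monthly urate reading will be requested".
- On the dietary substudy, "all patients in the active care arm will be invited to participate in a dietary modification substudy during the extension phase". The plan is "to be implemented over a period of time lasting up to three months". Those who opt in have this schedule: "Participants will be asked to perform weekly urate measurements, weight measurements and report on flares via the app".
- During flares: "The participant will be asked to enter additional urate readings and QoL information during flares". This sentence names no arm.
- For controls: "Participants of the control arm will continue as per routine care". No app reporting interval is given for them after week 52.
- At the week 104 and 156 visits the app diaries are reviewed, with no restriction by arm.

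**Analysis.** Section 8.2 does not say which app entries feed a between-arm comparison and sets no recall period.

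**The concern.** A count of self-reported flare days depends on how often people are asked and how far back they must remember. Here the asking differs by arm by design. Some active participants report every week or every two weeks for part of the extension, and no control does. Perfect compliance would not remove the difference, so this is separate from missed entries, and missing-data methods would not cure it. Adjusting for the number of entries would not cure it either, because the recall period per entry also differs.

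The reporting is densest around dose reduction, which is when the study most needs to know whether flares return. If frequent reporting picks up more flare days, the active arm could show an excess that comes from measurement, or a true benefit could be understated.

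Work days lost and appointments raise a different problem. They are endpoints at weeks 104 and 156, but the only stated prospective app collection of them ends at week 52.

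**Working it through.** **1. The plan's own extension figure.** Section 8.1 gives 81% power with 20 per arm and 94% with 30 per arm for adherence of 90% v 50%. The significance level is not restated for the extension, so I assume two-sided 5%, as for the original study. With the pooled-variance normal approximation,

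power = Φ{ [|p1 − p2| − 1.96·√(2·p̄(1 − p̄)/n)] / √([p1(1 − p1) + p2(1 − p2)]/n) }, where p̄ = 0.70.

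- n = 20: (0.40 − 1.96 × 0.1449)/0.1304 = 0.89, so power is 81.3%.
- n = 30: (0.40 − 1.96 × 0.1183)/0.1065 = 1.58, so power is 94.3%.

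The figure reproduces. It concerns adherence, and the plan gives no calculation for flare days, work loss or appointments.

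**2. The schedules side by side.**

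| Period or group | Active arm | Control arm |
|---|---|---|
| To week 52 | Monthly, four item types | Same |
| After week 52, remission with dose reduction | Disease activity data every two weeks until remission maintenance | None stated |
| After week 52, dietary opt-ins | Flares weekly, block of up to three months | Not invited |
| After remission maintenance | Monthly urate reading | None stated |
| Weeks 104 and 156 | Diary review | Diary review |

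Flares are named in the weekly dietary request. The two-weekly request refers to disease activity data without defining it. No intensified request names work days lost or appointments.

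**3. How large could the effect on flare days be?** The documents give no capture rates, so these are assumptions. Let cI be the share of flare days captured under intensive reporting, cM the share captured by monthly reporting, and f the fraction of active-arm time under intensive reporting. Assume that flares are spread evenly over time and that monthly capture applies to controls and to the rest of active-arm time. Then

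observed ratio = true ratio × [f·cI + (1 − f)·cM] / cM.

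The extension runs from week 52 to week 156, which is 104 weeks. A three-month block is about 13 weeks, so f = 13/104 = 0.125 if every active participant does one block.

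| Scenario | 95% v 85% | 90% v 75% |
|---|---|---|
| f = 0.125, one block for all | 86.25/85 = 1.015 | 76.875/75 = 1.025 |
| f = 0.25, plus an assumed further three months of two-weekly entry for all | 87.5/85 = 1.03 | 78.75/75 = 1.05 |
| f = 1, whole arm for 104 weeks | 95/85 = 1.12 | 90/75 = 1.20 |

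These are the ratios seen when the true ratio is 1.00. A true ratio of 0.80 would be seen as 0.81 to 0.82 in the first row, 0.82 to 0.84 in the second, and 0.89 to 0.96 in the third. The length of the two-weekly phase is not stated, so the second row is illustrative.

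**4. Direction.** If completeness is allowed to range over 80–100% in the active arm and 60–90% in controls, again by assumption, equal true rates give ratios from 0.80/0.90 = 0.89 to 1.00/0.60 = 1.67. That range includes values below 1.

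**The case against.** The strongest reply is that this asymmetry is narrow. Two-weekly entry covers only participants in remission who take up a dose reduction, and it ends at remission maintenance. Remission as defined in section 3.2 requires 12 months without flares, so these participants start with none recent. Weekly entry covers only dietary opt-ins, for a limited block. Routine care describes management and does not suspend outcome collection: outcomes are reviewed at 12, 24 and 36 months and diaries are reviewed in both arms. Section 8.2 names no test for flare days and gives no extension time point for work days or appointments.

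Most of this stands, and it rules out several inferences that a reader might draw:

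- *That the active arm as a whole reports intensively throughout.* The schedules apply to subgroups for limited periods, so ratios of 1.12 to 1.20 do not describe the arm-level comparison.
- *That work-loss and appointment counts are inflated in the active arm.* No intensified request names them. Including them under disease activity data would be a guess.
- *That the bias certainly runs against the active arm.* More frequent prompting usually captures more, but the documents contain no capture data.
- *That controls have no outcome collection after week 52.* Diary review at weeks 104 and 156 suggests that some is intended. It is simply not scheduled.

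What the reply does not answer is that annual review of diaries cannot equalise diaries filled on different schedules, and that nothing keeps the extra entries out of the between-arm counts. The sparse analysis text in section 8.2 is a reason to specify the comparison.

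**Conclusion.** The point holds in limited form. Followed as written, the plan collects flare reports more often in parts of the active arm than in controls after week 52, while flare days remain an endpoint at weeks 104 and 156. Flare days are therefore open to differential ascertainment, probably but not certainly to the active arm's disadvantage. For work days lost and appointments, the finding is that no common collection is stated beyond week 52.

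The size is unknown. Under the assumed capture rates it is about 1.5% to 2.5% if all active participants do one three-month block, and it reaches 12% to 20% only with whole-arm intensive reporting for two years, which no section describes. The smaller figures also assume that a monthly prompt continues in both arms, which the documents do not state.

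The week-24 primary endpoint and the week-52 comparisons are unaffected, because collection to that point is common to both arms. The extension's power calculation is unaffected because it concerns adherence. The point should be corrected before extension outcomes are compared, but it does not threaten the main result.

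**What to change.** In sections 6.1.4 and 6.2.3, state that the existing monthly app prompt continues in both arms through week 156, with the same items, wording and recall period. This has to come first, since no monthly outcome prompt is stated for either arm after week 52.

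In section 8.2, state that between-arm extension comparisons of flare days, work days lost and appointments use only those common monthly entries. Flag the additional weekly, two-weekly and during-flare entries in the app export and reserve them for within-arm monitoring.

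The cost is low: wording in three sections, an export flag, and continued use of an app and item set that already exist. No treatment changes. The downsides are that controls keep receiving prompts for two more years and that some active-arm detail is left out of the comparison. A small difference may remain, because someone who has just been reporting weekly may recall the month better, but the main difference in schedule and recall period is removed.

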6.2 STUDY ASSESSMENTS

6.2.1 History and physical examination

A focussed history and physical examination will be carried out at the specified time points. This includes basic anthropometrics weight, height, waist circumference and blood pressure. We will be recording the presence of tophi and take measurements of the largest tophus. Details of the duration of disease, frequency and pattern of flares will be recorded.

6.2.2 Laboratory assessments

Serum FBC, U&Es, LFTs, urate and oxypurinol levels will be collected by venepuncture.

6.2.3 App assessments

The smart phone application will collect the following data monthly over the 52 weeks of the study

- Number of days of self-reported gout flare
- Self-reported quality of life during/following gout flare evaluated using the EQ-5D-5L questionnaire
- Number of days lost at work due to gout flare
- Number of scheduled and unscheduled medical appointments/ hospital admissions due to gout

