3.2 Extension phase

Urate-lowering therapy requires a long term commitment from the patient and health care provider. We know that levels of medication adherence in gout are unusually low (Dehlin M, 2017 and Briesacher BA, 2008). A recent randomised controlled trial comparing specially trained nurses leading care versus usual care in the UK, showed that with dedicated surveillance and monitoring, the use of urate lowering therapy is significantly higher at 1 and 2 years in the nurse-led compared to the usual care group (Doherty M, 2018). The GoutSMART approach may provide an alternative means for patients to monitor their disease and increase awareness of the role and importance of long-term urate lowering therapy for disease control thereby increasing adherence. At the 12 month study visit all participants will be invited to participate in a 2 year extension to the study which will evaluate long term compliance with medication along with clinical outcomes. Additional participants will be invited to take part in

this long term monitoring arm of the study and will be randomised 1:1 to active monitoring or routine care. All participants taking part in this extension study will have their medication optimised using the GoutSMART approach to ensure that their urate level is at target of 0.3mmol/l or less.

For participants in the active care arm of the study ongoing monitoring of self-reported urate will be performed until participants meet criteria for disease remission. For the purposes of this study we will define disease remission to have been achieved if all three of the following outcomes have been achieved:

[figure not shown]
- 1) Resolution of clinically evident tophi
- 2) Urate levels at or below 0.3mmol/l over preceding 12 months (with minimum of 3 separate readings obtained in different months).
- 3) Resolution of gout flares (self-reported) for 12 months

When remission has been achieved by these criteria then participants will be given the option to reduce their dose of allopurinol in line with current best practise guidelines which suggest that maintaining urate below 0.36 mmol/l is sufficient to maintain remission, and that long term urate levels should not be held below 0.18mmol/l.

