
Participants will be invited to the RDU clinic, or alternatively if hospital attendance is not appropriate due to recommendations to self-isolate or maintain social distancing due to the coronavirus pandemic then this assessment will be made by telephone. The patient diaries generated by the GoutSMART application will be reviewed and any adverse advents recorded. Participants will complete a questionnaire on their experience with standard care or the testing device and the smart phone application. All participants will be asked to record the number of doses of medication missed in the preceding 2 weeks. A physical examination will be performed to assess the size and number of tophi, or submitted images will be reviewed. Finger prick and/or serum urate will be measured along with blood tests of full blood count, renal and liver function tests and oxypurinol levels. A letter will be written to the GP of all participants summarising the disease course and management throughout the past 24 weeks and proposing further management advice. All participants will retain access to the smart phone application and be asked to enter information about the disease course on a monthly basis until week 52.

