7 DATA COLLECTION

Data will be collected at baseline, week 24 and 52 visits as well as via the smart phone application on a monthly basis. Data will be collected by the principal investigator and the sub-investigators. We will use the EQ-5D® standardized instruments EQ-5D-5L to evaluate health outcome. To maximise completeness of data collection, every effort will be made to contact participants who have failed to attend scheduled visits, submit requested information via the smart phone application or return questionnaires. Participants will be contacted by telephone on at least two occasions.

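### Monthly app collection of flares, quality of life, work loss and appointments is written to stop at week 52, although the same endpoints are assessed at weeks 104 and 156 and the extension schedule is incomplete

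*Combined protocol and SAP*

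**What the plan says.** **Where collection stops.** Section 6.2.3, which defines what the app gathers, opens: "The smart phone application will collect the following data monthly over the 52 weeks of the study". It then lists flare days, EQ-5D-5L, work days lost, and appointments or admissions. Section 6.1.3 agrees: after the week 24 visit all participants are "asked to enter information about the disease course on a monthly basis until week 52".

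**Where the endpoints go on.** Section 2.2.2 describes its secondary endpoints as "assessed at week 24 and 52, and for extension study also at week 104 and 156". The flare endpoint reads "Prospectively gathered number of days of self-reported gout flare over course of study", and the quality-of-life, work-loss and appointment endpoints are likewise to be gathered prospectively over the whole study.

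**What the extension text provides.** Section 6.1.4 covers the visits at weeks 52, 104 and 156, and has the app diaries reviewed at them. It describes three kinds of app entry:
- Intervention participants in remission enter disease activity data (not defined) every two weeks until remission maintenance.
- During flares, "The participant will be asked to enter additional urate readings and QoL information during flares".
- Participants in the dietary substudy report flares through the app. Section 3.2 offers that substudy to the active arm only.

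The control arm is said to continue with routine care. Section 6.2.4 adds study-specific questionnaires at weeks 104 and 156, without giving their content.

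**The general statement.** Section 7 begins "Data will be collected at baseline, week 24 and 52 visits" and adds monthly app entry with no end date.

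**The concern.** Sections 6.2.3 and 6.1.3 give an explicit end date for monthly entry that falls two years before the last assessment of the same endpoints. Section 6.2.4 was extended to weeks 104 and 156 while section 6.2.3 was not, which suggests an incomplete update rather than a decision to stop.

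Three things are at stake.

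1. **Completeness.** Monthly prospective counts that are never requested cannot be recovered later. A yearly visit or questionnaire of unstated content cannot be assumed to replace them.
2. **Comparability.** The app entry that section 6.1.4 does describe is mainly for the active arm. Self-reported counts depend on how often people are asked. If one arm is prompted and the other is not, a difference may reflect the asking. The direction of that bias cannot be predicted. Section 8.2 plans between-group tests for work loss and appointments.
3. **Remission.** The third criterion in section 3.2 is "Resolution of gout flares (self-reported) for 12 months". It decides who is offered the dose-reduction option and so feeds the dose-reduction endpoint. Active-arm participants not yet in remission have ongoing urate monitoring in section 3.2, but sections 3.2 and 6.1.4 set no flare-entry schedule for them after week 52 outside flares and the dietary substudy.

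**Working it through.** **Inputs.** Follow-up is 1 year plus 2 further years in the extension (study summary), with the last visit at week 156 (sections 2.2.2 and 6.1.4). Monthly app entry ends at week 52 (sections 6.2.3 and 6.1.3).

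**Step 1: total follow-up.** 52 + 104 = 156 weeks, which agrees with the plan's last visit.

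**Step 2: share after the stated stop, for a participant followed from original baseline.** (156 − 52) / 156 = 104 / 156 = 66.7%. At 12 entries per year over 2 years, that is 2 × 12 = about 24 monthly entries.

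**Step 3: participants recruited directly into the extension (sections 3.2 and 4.1).** The plan does not say what the 52 weeks mean for them, nor state their follow-up length separately. Assuming 104 weeks:
- if their own first 52 weeks count, the uncovered share is (104 − 52) / 104 = 50%;
- if they do not count, it is 104 / 104 = 100%.

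The 67% therefore cannot be applied to this group.

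**Step 4: item by item after week 52.**

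| Item | Endpoint at weeks 104 and 156 (2.2.2) | Monthly entry ends at week 52 (6.2.3) | App entry named for the extension (6.1.4) | Test named in 8.2 |
|---|---|---|---|---|
| Flare days | Yes | Yes | Partial: undefined disease activity data (intervention, in remission); flare reports (dietary substudy) | None |
| EQ-5D-5L | Yes | Yes | Partial: quality of life during flares, instrument not named | Not analysed directly |
| Work days lost | Yes | Yes | Not named | t-test or Mann-Whitney |
| Appointments, admissions | Yes | Yes | Not named | t-test or Mann-Whitney |

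Two of the four items have partial entry and two have none named. Section 6.1.4 gives no explicit app entry for the control arm on any item, although its sentence on entry during flares could be read as covering both arms.

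**Step 5: effect on power.** None. The original sample size rests on the urate target at 24 weeks. The extension figures (81% with 20 per arm, 94% with 30 per arm) rest on adherence of 90% against 50%. Neither uses these items.

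**The case against.** The strongest reply is that the plan does provide for these data after week 52, and that only two sentences are out of date.

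- Section 6.1.4 reviews app diaries at weeks 104 and 156 without restricting this to one arm.
- Section 6.1.2 prompts all participants monthly for flare days, quality of life, work loss and appointments, with no end date.
- Section 3.1 gives controls an app version for entering flares and quality of life through the trial.
- Section 6.2.1 records flare frequency and pattern at the specified time points, and section 6.2.4 adds questionnaires.

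Much of this stands, and it rules out several stronger readings that a reader might infer:

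- **That these endpoints have no data source after week 52.** The diary review, the partial entries and the visit records are stated sources.
- **That section 7 also stops monthly collection at week 52.** Only its visit list ends there.
- **That usual care will be followed by yearly recall, so the comparison is biased.** No section says so. Continuing with routine care can describe treatment rather than data entry. Unequal ascertainment is a risk of following the text, not a stated design.
- **That the remission criterion biases the comparison between arms.** Section 3.2 applies it to the active arm only. The issue is whether it can be judged there.

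The reply does not remove the conflict. A diary reviewed at week 156 needs entries that sections 6.2.3 and 6.1.3 stop requesting at week 52. Section 6.1.2 was written around the original study, and its open-ended prompt is weaker than two sections that give an end date.

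**Conclusion.** The concern holds as an internal conflict combined with an incomplete extension schedule. Sections 6.2.3 and 6.1.3 end monthly entry at week 52; sections 2.2.2 and 6.1.4 need it to week 156. Work loss and appointments have no stated schedule after week 52, and the control arm has no explicit extension entry.

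The size is 104 of 156 weeks (67%, about 24 monthly entries) for participants followed from original baseline. For direct recruits it is undefined: 50% or 100% of an assumed 104 weeks, depending on how the window is read.

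The consequences are limited. Section 8.2 treats these outcomes as exploratory, does not analyse quality of life directly and names no test for flare days. The exposure to unequal ascertainment in a planned test therefore lies mainly with work loss and appointments. The primary result at 24 weeks and all power figures are unaffected. The correction is still worth making, because following the text as written could lose data for good.

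**What to change.** - **Section 6.2.3:** state that the same monthly app items continue to week 156, or to the end of extension follow-up for participants recruited directly into it, in both arms, with the same schedule and wording. State what the collection window is for direct recruits.
- **Section 7:** add the week 104 and 156 visits.
- **Sections 6.1.3 and 6.1.4:** reconcile them with this. Remove the week 52 limit for extension participants, define disease activity data, and say that entries during flares are in addition to the monthly items and whether they apply to both arms.

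The app and its prompts already exist, so this is mainly a change of wording. The burden is about 24 further short monthly entries per extension participant. No sample size or analysis needs to be recalculated.
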